6.2. Number of Volunteers

The study population will consist of 60 healthy volunteers without HIV-1 infection who are available for at least 48 weeks of follow-up. Individuals of all races and groups may participate as long as the inclusion/exclusion criteria are met. The inclusion/exclusion criteria have been chosen to minimize risk to all participants. Therefore, those individuals with conditions that might place them at increased risk have been excluded.

Pregnant women and children are excluded from the trial as the safety of this vaccine has not previously been evaluated in humans and the effects on children or the unborn child are not known.

6.3. Treatment Assignment

The volunteers in this study will enroll in each group of the study sequentially as this is a dose escalation study. Each volunteer will undergo randomization as described in [Section 8.4](#). Each group will be fully enrolled prior to the enrollment of the next group. The description of the FLSC vaccine is noted in [Section 8](#) and [Section 9](#) and the clinical formulation of the products are listed in [Section 9](#). Volunteers in all arms will be immunized by intramuscular injection on Days 0, 28 (week 4), 56 (week 8), and 168 (week 24). Following completion of the immunization schedule, all volunteers will be followed (for an additional 24 weeks) until the end of the trial at 48 weeks as detailed in [Section 6.1.1.3](#).

6.4. Dose Escalation Criteria

Requirements to begin immunizations in the higher dose groups (Groups 2 and 3) are listed below.

1. Safety data including the visit 4 data (2 weeks after the second immunization) in the 20 volunteers in the lower dose group has been collated and then reviewed by the DSMB.
2. DSMB review is completed, no safety concerns are noted, and approval to enroll the next group is granted.

6.4.1. Safety Criteria for Adjustment or Stopping Doses

1. If more than 5 volunteers in any group have an unexplained CD4 cell count decline (confirmed by assays at least 4 weeks apart) of greater than 30 percent and corroborated by a similar CD4% decline (>30%), immunizations in that study group will be stopped. No further immunizations will be allowed until after all data are reviewed by the IHV DSMB and the DSMB authorizes immunizations to continue in this group. Follow-up visits for safety will continue during this time. Note that an unexplained drop in CD4 cell count is defined as a decline that cannot be explained by an intercurrent illness or other event known to cause decreased CD4 cell counts.
2. The entire study will be stopped if five or more vaccine related severe (grade 3 or 4) adverse events occur in any group.
3. The volunteer will have immunizations stopped upon the occurrence of an unexpected Grade IV event felt by the investigator to be related to the study vaccine. No further immunizations will be allowed until after all data are reviewed by the IHV DSMB and the DSMB authorizes immunizations to continue in this group. Follow-up visits for safety will continue during this time.
4. The entire study immunizations will be stopped upon the occurrence of one unexpected serious adverse event felt to be related to the study vaccine.

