6.5. Criteria for Study Termination

Criteria for Termination of Study immunizations in all volunteers.

1. The entire study will be stopped upon the occurrence of an unexpected Grade 3 or 4 event thought to be related to the study vaccine in 5 volunteers as noted in [Section 6.4.1](#). If after review by the DSMB, these events are determined by the DSMB to be study vaccine related, the volunteers would be continued to be followed on the study for safety, but no further immunizations would occur in any of the groups.
2. Individual volunteers may have immunizations halted as listed in [Section 6.4.1](#).

Table 3: Study Design

Phase 1 FLSC Study Immunization Schedule/Volunteer Allocation							
Group	Route of Administration	N Vaccine/Control	Vaccine Dose	Vaccination Schedule in Months (Days)			
				0	1(28)	2(56)	6(168)
1	IM	15	0.25 ml (75 ug)	FLSC/ ALPO4	FLSC/ ALPO4	FLSC/ ALPO4	FLSC/ ALPO4
		5	0.25 ml	Saline	Saline	Saline	Saline
2	IM	15	0.5 ml (150 ug)	FLSC/ ALPO4	FLSC/ ALPO4	FLSC/ ALPO4	FLSC/ ALPO4
		5	0.5 ml	Saline	Saline	Saline	Saline
3	IM	15	1.0 ml (300 ug)	FLSC/ ALPO4	FLSC/ ALPO4	FLSC/ ALPO4	FLSC/ ALPO4
		5	1.0 ml	Saline	Saline	Saline	Saline
TOTALS		60					

Table 4: Schedule of Assessments

STUDY VISIT	0	01	02	03	04	05	06	07	08	09	10	11	12	13	14 ³				
STUDY DAY	-30 TO -3	0	1-2	14	28	29-30	42	56	57-58	70	84	112	168	169-170	182	196	252	294	336
STUDY WEEK	-4 TO -0	0	2	4	6	8	10	12	16	24	26	28	36	42	48				
Informed Consent	X																		
Immunization		X		X		X		X				X							
Complete Medical History and Physical Examination	X																		X
Interval Medical History and Directed Physical Examination(as indicated)		X		X	X		X	X		X	X	X	X		X	X	X	X	
Phone Interview			X			X			X					X					
Dispense diary		X			X			X					X						
Monitor Adverse Events		X	X	X	X	X	X	X	X	X	X	X	X	X	X	X	X	X	X
Blood for Screening Labs: CBC with diff Serum Chemistry, LFT's PT/PTT Hepatitis B Surface Antigen Hepatitis C Antibody ¹ CD4 cell count HIV-1 RNA PCR HIV-1 ELISA/Western blot	X																		X
Pregnancy Test (serum)	X																		
Pregnancy Test (urine)		X			X			X					X						X
Urinalysis	X																		X

STUDY VISIT	0	01		02	03		04	05		06	07	08	09		10	11	12	13	14 ³
Blood for Safety Labs: CBC with diff Serum Chemistry, LFT's CD4 cell count HIV-1 RNA PCR ²		X		X	X		X	X		X	X	X	X		X	X	X	X	
Blood for Serologic Assays/Serum storage	X	X ⁴		X ⁴	X ⁴		X ⁴	X ⁴		X ⁴	X	X ⁴	X ⁴		X ⁴	X	X ⁴	X	X ⁴

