7.3.3. Reasons to Halt Study

If 5 or more volunteers in any group have an unexplained CD4 cell count decline (confirmed by assays at least 4 weeks apart) of greater than 30 percent and corroborated by a similar CD4% decline (>30%), immunizations in that study group will be stopped. No further immunizations will be allowed until after all data are reviewed by the IHV DSMB and the DSMB authorizes immunizations to continue in this group. Follow-up visits for safety will continue during this time. Note that an unexplained drop in CD4 cell count is defined as a decline that cannot be explained by an intercurrent illness or other event known to cause decreased in CD4 cell counts. Other reasons are noted in [Section 6.4.1](#) and [Section 6.5](#).

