7.3.4. Reasons for Discontinuation of all Immunizations in the Study

All immunizations across the entire study will be stopped upon the occurrence of 5 or more unexpected Grade 3 or 4 events felt to be related to the study vaccine in any group or a serious adverse event felt to be related to study vaccine in one volunteer as noted in [Section 6.4.1](#) and [Section 6.5](#). Follow-up visits for safety will continue to occur as per study protocol. No further enrollments will occur.

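### The automatic stopping rules for CD4 decline and for vaccine-related grade 3/4 events carry different thresholds in Sections 6.4.1, 6.5, 7.3.3 and 7.3.4

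*Combined protocol and SAP*

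**What the plan says.** **CD4 decline.** Section 6.4.1 item 1 begins "If more than 5 volunteers in any group have an unexplained CD4 cell count decline"; Section 7.3.3 begins "If 5 or more volunteers in any group have an unexplained CD4 cell count decline". Both require a fall of more than 30% in count, confirmed at least 4 weeks apart and matched by the CD4 percentage. Both stop the group until the DSMB authorizes resumption.

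**Related grade 3/4 events.** Three sections state a study-level stop:

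- Section 6.4.1 item 2: "The entire study will be stopped if five or more vaccine related severe (grade 3 or 4) adverse events occur in any group". Expected and unexpected events both count.
- Section 6.5 item 1: "an unexpected Grade 3 or 4 event thought to be related to the study vaccine in 5 volunteers". It cites Section 6.4.1 but sets no group limit of its own. It adds a conditional step, "If after review by the DSMB, these events are determined by the DSMB to be study vaccine related", after which participants stay in safety follow-up "but no further immunizations would occur in any of the groups".
- Section 7.3.4: "5 or more unexpected Grade 3 or 4 events felt to be related to the study vaccine in any group". It cites Sections 6.4.1 and 6.5, stops all immunizations without condition, and closes enrollment.

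**Related serious adverse event.** Section 6.4.1 item 4 requires the event to be unexpected. Section 7.3.4 does not attach that word to the serious event, though it cites Section 6.4.1.

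**Links between the rules.** Section 7.3.3 ends with "Other reasons are noted in" Sections 6.4.1 and 6.5, and Section 13.7 points to Sections 6.4.1, 6.5 and 7.3.

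**The concern.** A stopping rule should give the same answer wherever it is read. Here the same count can require a stop in one section and not in another. Sections 6.5 and 7.3.4 present their rules as those of Section 6.4.1 yet differ from it, so they look like inexact restatements rather than deliberate extra triggers.

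The CD4 rule matters most. Section 4.5.2 names possible autoimmunity to CD4 as the risk that shaped the safety design, and this is the group-level stop tied to it. Someone holding only Section 6.4.1 would continue a group with 5 confirmed declines. On the nominal visit schedule the first 4-week confirmation is possible at Day 42 (Day 14 plus 28 days), so a volunteer's third and fourth injections are the ones at stake. For grade 3/4 events, the choice of unit and scope decides whether the whole study stops.

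**Working it through.** The plan gives no operating characteristics for its stopping rules, so there is no stated figure to reproduce. The check has two parts.

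**1. The grade 3/4 wordings applied to the same data.** No rates are needed. All events below are related and grade 3 or 4.

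| Scenario | 6.4.1 item 2 | 6.5 item 1 | 7.3.4 |
|---|---|---|---|
| One group: volunteer A has 3 events, volunteer B has 2; total 3 + 2 = 5 events in 2 volunteers | Stop | No stop (2 volunteers, fewer than 5) | Stop only if all 5 are unexpected |
| One group: 5 volunteers with one expected event each | Stop | No stop | No stop |
| Three groups: 2 + 2 + 1 = 5 volunteers with one unexpected event each | No stop (at most 2 in a group) | Stop if read study-wide; no stop if the citation of 6.4.1 imports its group limit | No stop |

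If all triggers are applied together, the grade 3/4 rule in Section 7.3.4 never acts first: it has the same unit and scope as Section 6.4.1 item 2 and counts a subset of the same events. Section 6.5 adds a stop only when the 5 volunteers are spread over groups.

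**2. CD4 rule.**

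Inputs: 15 vaccine and 5 placebo recipients per group (Section 4.2 and Table 3), hence 20. Thresholds are 5 (Section 7.3.3) and 6, that is, more than 5 (Section 6.4.1). The rate p is an assumption: the probability that a volunteer has a confirmed, unexplained decline while the group still has injections due.

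With X ~ Binomial(n, p), the two versions differ by P(X = 5) = C(n,5) p^5 (1 − p)^(n−5).

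- n = 15, p = 0.10: 3003 × 0.1^5 × 0.9^10 = 0.0105
- n = 15, p = 0.20: 3003 × 0.2^5 × 0.8^10 = 0.1032
- n = 20, p = 0.10: 15504 × 0.1^5 × 0.9^15 = 0.0319
- n = 20, p = 0.20: 15504 × 0.2^5 × 0.8^15 = 0.1746

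Probability of stopping one group:

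| Assumed p | n = 15: 5 or more | n = 15: more than 5 | n = 20: 5 or more | n = 20: more than 5 |
|---|---|---|---|---|
| 5% | 0.06% | 0.01% | 0.26% | 0.03% |
| 10% | 1.3% | 0.2% | 4.3% | 1.1% |
| 20% | 16.4% | 6.1% | 37.0% | 19.6% |
| 30% | 48.5% | 27.8% | 76.2% | 58.4% |

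The n = 15 columns fit a pure vaccine effect. The n = 20 columns fit declines that can occur in anyone; the rule counts all volunteers in a group, and Section 11.6 has the DSMB review blinded data. No probability is given for the grade 3/4 rule, because it would depend mainly on an assumed number of severe events per affected volunteer.

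**The case against.** The strongest reply is that nothing here permits dosing to continue. Each rule says when to stop, none says to carry on below its threshold, and the cross-references in Sections 7.3.3 and 13.7 present the rules as a set. Obeying all sections means stopping at 5 CD4 declines. This stands. A reader might infer from the absence of an explicit any-trigger sentence that the protocol leaves the stop undecided or allows dosing at 5. The documents do not support that. What remains is the risk of applying one section in isolation.

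Other stronger readings also fail or are weak:

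- **Enrollment.** That only Section 7.3.4 closes enrollment is true literally, but Sections 6.4.1 item 2 and 6.5 stop the whole study, which covers enrollment.
- **Serious events.** The missing word in Section 7.3.4 may carry over from earlier in its sentence or from the cited Section 6.4.1. Its effect depends on the Investigator's Brochure, which is not among the documents.
- **Scope of Section 6.5.** A study-wide count is possible, but its citation of Section 6.4.1 may import the group limit. The text does not settle it.

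Oversight limits the harm. Under Section 11.6 the DSMB meets about every 3 months, before each escalation and ad hoc, is told of serious related events within 48 hours, and can halt the study. Section 7.3.1.1 withdraws from dosing any volunteer with a related grade 4 or serious event, and Section 11.5.1 expects most related grade 3 events to end that volunteer's dosing. The 48-hour notice does not cover a tally of CD4 declines or non-serious grade 3 events, so it does not replace a clear numerical trigger.

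**Conclusion.** The inconsistency is real and in the current text, and it should be fixed. It is a conflict between thresholds, not the absence of a stopping rule. For CD4 it bites only at exactly 5 volunteers: a gap of about 1 to 3 percentage points in the chance of stopping a group at an assumed 10% rate, about 10 to 17 points at 20%, and negligible at 5%. Those figures assume independent volunteers with a common rate, and the documents supply no rate. For grade 3/4 events the conflict needs no rate: five related severe events in two volunteers of one group stop the study under Section 6.4.1, do not under Section 6.5, and do under Section 7.3.4 only if all five are unexpected. The serious-event wording is minor and only needs confirming.

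**What to change.** 1. In Section 6.4.1 item 1, replace more than 5 with 5 or more, to match Section 7.3.3.
2. State the grade 3/4 rule once, in Section 6.4.1, with one unit (events or volunteers), one scope (any group or study-wide) and a clear statement of whether the event must be unexpected. The sponsor and DSMB should choose these. Sections 6.5 and 7.3.4 should then refer to that rule without restating it.
3. Until then, apply every existing trigger and remove or soften none. In particular, the DSMB step in Section 6.5 should not be used to make the unconditional stop in Section 7.3.4 conditional.
4. Have the sponsor confirm whether the serious-event rule requires the event to be unexpected.

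The cost is a formal amendment with sponsor and IRB approval (Section 17); sample size, visits and assays do not change. The downside is a somewhat higher chance of a group pause than under Section 6.4.1 read alone, as tabulated above. In addition, under Section 6.4.1 item 2 as it stands, five expected severe reactions in one group stop the whole study; the sponsor and DSMB should confirm that this is intended when they choose the rule.

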4.5.2. Potential Risks

In theory, it is possible that immunization with gp120-CD4 complexes could induce auto-anti-CD4 responses. These could be antibody responses, T cell responses, or both. It is well established in the older immunological literature that it is possible to break tolerance to self-antigens by adding T helper epitopes. In principle, gp120 T helper epitopes could collaborate with auto-anti-CD4 B cells or CTL precursors to break tolerance to CD4 epitopes. In this regard, it is interesting to note that immunization of a chimp with soluble human CD4 elicited an antibody response against an epitope that is not present on cell surface CD4 although the sera were able to block infection of chimpanzee or human lymphocytes with HIV-1 (Watanabe, Boyson et al. 1992). Similar results were obtained in rhesus macaques immunized with human CD4 (Watanabe, Chen et al. 1991; Watanabe, Levine et al. 1991). These studies used soluble human CD4 that differs in the extracellular domain from chimp CD4 by 4 residues and macaque CD4 by 37 residues raising the question of whether tolerance was actually broken in these studies and whether it would be broken if macaques were deliberately immunized with human CD4. Deliberate immunization of cynomolgus macaques with human CD4 showed that the antibody response was selectively directed against human epitopes (Truneh, Frescatore et al. 1990). We were able to verify this result

in our immunotoxicology study using FLSC ([Study Number VTR-0018](#)). There was no evidence in this study that immunization of cynomolgus macaques with a homologous CD4 contained in rhFLSC broke tolerance. While these findings strongly indicate that the CD4 moiety of FLSC will be poorly immunogenic in humans, the risk of inducing auto-anti-CD4 antibodies drives the design of the phase 1 safety studies.

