It is worthwhile to consider what would happen if an auto-anti-CD4 antibody response occurs in a clinical setting. In this regard, the expanding literature on the therapeutic use of anti-CD4 antibodies is informative. There are two non-exclusive mechanisms whereby passive immunization with anti-CD4 antibodies modulates disease. First, some anti-CD4 antibodies cause depletion of CD4+ T cells that is variable in duration as a function of the protocol and isotype of the antibody ([Mourad, Preffer et al. 1998](#); [Mason, Aldrich et al. 2002](#)). Alternatively, anti-CD4 antibodies can coat CD4+ T cells without depleting them from the peripheral circulation ([Mourad, Preffer et al. 1998](#); [Mason, Aldrich et al. 2002](#)). In both cases, clinical effects can be observed ([Larche, Robinson et al. 2003](#)) but there is evidence in rheumatoid arthritis that coating is more important than depletion for clinical effect ([Mason, Aldrich et al. 2002](#)). Very recently, non-depleting anti-CD4 antibodies that block HIV-1 infection in vitro have been developed for passive immunization against HIV-1 ([Reimann, Khunhkhun et al. 2002](#)). Thus, it is reasonable to expect that if immunization with FLSC were to break tolerance to CD4 both depleting and non-depleting anti-CD4 antibodies are possible outcomes. Each of these possibilities were addressed in the immunotoxicology study ([Study Number VTR-0018](#)). No autoimmune responses to CD4 after repeated immunization with FLSC or rhFLSC were observed.

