6.1.1. Study Procedures

6.1.1.1. Study Entry

Volunteers who satisfy the entry criteria will be fully informed about the study by the investigator or his/her designee and asked whether they wish to participate. The information given to the patient or his/her legal representative will be in a language understandable to the volunteer or the representative. All questions will be answered prior to the volunteer signing consent. Written consent will be obtained from the volunteer or his/her legal representative prior to performing any study related procedures. This includes obtaining consent for the acquisition and review of the volunteer's prior medical history (and old medical record if appropriate and available). A copy of the informed consent will be given to the volunteer or his/her legal representative.

All volunteers having completed informed consent procedures will undergo a baseline screening evaluation within 30 days of initial immunization with the experimental candidate vaccine (or placebo). The CD4 cell count will be repeated on the day of initial immunization. These two observation points will define protocol baseline evaluation.

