7. SELECTION AND WITHDRAWAL OF VOLUNTEERS

7.1. Volunteer Inclusion Criteria

All of the following inclusion criteria must be fulfilled for patients to be eligible for participation in the proposed clinical protocols.

1. Age: 18 to 45 years of age.
2. Sex: Male or Female (female volunteers of child-bearing potential must have a negative serum beta human chorionic gonadotropin (pregnancy) test at time of screening and entry into the study and provide assurance of the use of effective (as judged by the investigator) birth control methods or abstinence beginning at least 60 days prior to the study and during the study)
3. Documented HIV-1 seronegative by ELISA
4. Be in good general health without clinically significant medical history, physical examination findings, or clinically significant abnormal laboratory results (i.e., chronic medical conditions as noted in the exclusion criteria such as cancer as well as any conditions that in the opinion of the investigator might pose a risk to the volunteer)
5. No identifiable risk factor for acquisition of HIV infection (i.e., intravenous drug use/needle sharing, unprotected sex with multiple partners)
6. Negative b-HCG pregnancy test on the day of initial vaccination (women only);
7. Negative screen for Hepatitis B surface antigen (HBsAg);
8. Negative screen for antibodies to Hepatitis C virus (Patient may enroll if patient can provide documentation of negative HCV PCR.)
9. Participant must have a CD4 count within the normal range of the clinical laboratory utilized for the study and a CD4 percentage within 20% of the normal range of the clinical laboratory
10. Laboratory parameters must be within pre-specified limits as defined by exclusion criteria.
11. Volunteers must be willing and able to provide written informed consent to participate in the study.
12. Available for at least 48 weeks of follow-up.

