9.5. Administration

Immunizations will be administered on an outpatient basis on Day 0, Day 28, Day 56, and Day 168. Evaluations listed on the study schema will be conducted prior to immunization with the study vaccine. Total time required in the clinic for an immunization visit will be approximately one hour, unless the subject experiences an Adverse Event which requires additional treatment. The volunteer will be instructed to call a designated staff member immediately if an Adverse Event should occur after the volunteer leaves the clinic.

The intramuscular route will be used in all cases. At all stages of the preparation, aseptic procedures must be followed. After cleansing the site of injection with a suitable antiseptic, the injections will be given as an intramuscular injection in the deltoid muscle of the volunteer's non-dominant arm (unless preferred otherwise by the patient) with a 22 gauge 25 mm (1 inch) needle. All of the product contained in the syringe will be injected. As noted in [Section 9.4](#), according to the group number, drug product or diluent will be given as an intramuscular injection in the deltoid muscle of the volunteer's non-dominant arm per institutional protocol. The study vaccine may be given in the deltoid muscle of the dominant arm at the investigator's discretion (e.g., open wound near/on the proposed injection site, request of the volunteer, etc.). Immediately after injection, the subject will be observed closely for 30 minutes. Complete vital signs will be recorded prior to administration, at 15 minutes and 30 minutes post-injection. Injection site evaluations will be recorded at 15 minutes and 30 minutes post-injection. The volunteer will be instructed in the evaluation of these local reactions; study personnel will observe and instruct while the volunteer takes his/her own temperature at Visit 1 (as guide for subsequent evaluations. Volunteer diary card for immunization reactions will be dispensed and instructions for its completion will be given.

If there are no clinically meaningful abnormalities and the volunteer has no complaints which are considered cause for concern by the Principal Investigators or his designee, he/she may leave the clinic with instructions to immediately call a designated staff member should any complications arise. If there are any local or systemic reactions present, the volunteer will be asked to return to the clinic the following day for a follow-up visit.

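### Under selective CD4 depletion without replacement, the CD4% condition makes the >30% CD4 halting rule act at a count loss of about 40–49%; a matched CD4% cut-off is a cheap improvement

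*Combined protocol and SAP*

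**What the plan says.** Section 4.5.2 states that "the risk of inducing auto-anti-CD4 antibodies drives the design of the phase 1 safety studies". It notes that "some anti-CD4 antibodies cause depletion of CD4+ T cells that is variable in duration", and names coating of CD4+ cells without depletion as the other possibility.

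The pre-set response is Section 6.4.1 item 1. A volunteer counts towards it with an "unexplained CD4 cell count decline (confirmed by assays at least 4 weeks apart"), and more than 5 such volunteers are needed in a group. The size of fall required on each measure, and the consequence, are set as follows: "of greater than 30 percent and corroborated by a similar CD4% decline (>30%), immunizations in that study group will be stopped". Section 7.3.3 repeats both cut-offs but asks for 5 or more volunteers. Dosing then waits for DSMB review.

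For baseline, CD4 is measured at screening and on Day 0: "These two observation points will define protocol baseline evaluation" (Section 6.1.1.1). Doses fall on "Days 0, 28 (week 4), 56 (week 8), and 168 (week 24") (Section 6.3). Table 4 schedules CD4 counts on Days 14, 28, 42, 56, 70, 84 and 112 between the first and fourth dose days. On dosing days, "Evaluations listed on the study schema will be conducted prior to immunization with the study vaccine" (Section 9.5).

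The plan gives no reason for using one cut-off on both measures, and no operating characteristics for the rule. It gives no baseline CD4% figure either: Section 7.1 asks only for "a CD4 percentage within 20% of the normal range of the clinical laboratory". Appendix 2 has no CD4 row.

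**The concern.** The rule reads as a 30% rule, with CD4% there to confirm that a low count is genuine. But CD4% is CD4 cells divided by all lymphocytes. When only CD4 cells are lost, the denominator shrinks too, and CD4% falls by less than the count. A >30% condition on CD4% is then the stricter of the two and sets the level at which the rule acts.

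At stake is the only numerical CD4 halting criterion for the risk that the protocol puts at the centre of its safety design. If depletion is selective and lost cells are not replaced, losses between 30% and roughly 40–49% may not trigger the pause before dose 4. Any pause in that range rests partly on assay noise and discretion.

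**Working it through.** **Inputs from the protocol.** Count fall >30% and CD4% fall >30%; assays at least 4 weeks apart; 15 vaccine and 5 placebo recipients per group; draw days as in Table 4; baseline taken as the mean of screening and Day 0. The protocol states no figure for this rule's performance, so there is none to reproduce.

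**Assumptions (not in the protocol).** Baseline CD4% p = 35–55% of lymphocytes. Within-person CV for count/CD4% of 10/5, 15/7.5 or 20/10%. Share r of lost CD4 cells replaced by other lymphocytes, from 0 to 1. CD4% decline read as relative.

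**Step 1: algebra, no noise.** If a fraction f of CD4 cells is lost:

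- CD4% afterwards = p(1−f) / (1 − pf(1−r)).
- With r = 0, the relative fall at f = 0.30 is 1 − 0.7/(1 − 0.3p). For p = 0.45: 1 − 0.7/0.865 = 19.1%.
- The CD4% condition is first met at f = 0.3 / (1 − 0.7p(1−r)). For p = 0.45, r = 0: 0.3/0.685 = 43.8%.

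| p | CD4% fall at 30% count loss | CD4% fall at 35% count loss | Loss that meets both conditions, r = 0 | Same, r = 0.5 |
|---|---|---|---|---|
| 35% | 21.8% | 25.9% | 39.7% | 34.2% |
| 45% | 19.1% | 22.8% | 43.8% | 35.6% |
| 55% | 16.2% | 19.5% | 48.8% | 37.2% |

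With r = 1 the denominator does not change and the two cut-offs coincide at 30%.

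**Step 2: add noise.** Simulation with lognormal errors, independent between visits and between the two measures. All 15 vaccinees have a 35% loss from Day 14, r = 0. Both conditions are required at two draws at least 28 days apart, and at least 5 volunteers must qualify. Chance of a pause by Day 112, over the three CV pairs:

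| p | Present rule |
|---|---|
| 35% | about 20–67% |
| 45% | 0.05–24% |
| 55% | 0–3% |

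Sensitivity at p = 45%, by Day 112 unless stated:

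- The text ties the 4-week confirmation to the count and leaves CD4% open. If one low CD4% is enough: 18–94%.
- More than 5 volunteers (Section 6.4.1): 0–10% with both draws.
- Day 168 pre-dose draw counted: 0.2–37%.
- Count and CD4% sharing errors: 0.3–56%.
- A quarter of lost cells replaced: 29–72%. Half replaced: at least 96% (83–90% at p = 55%).

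**Step 3: matched cut-off.** Same 35% loss and r = 0, with the CD4% cut-off set to 1 − 0.7/(1 − 0.3p) and required at both draws; at least 5 volunteers, by Day 112, range over p and CV:

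| Scenario | Present rule | Matched cut-off |
|---|---|---|
| All 15, onset Day 14 | 0–67% | about 99.9–100% |
| All 15, onset Day 42 | 0–28% | 96–100% |
| All 15, onset Day 70 | 0–2% | 47–95% |
| 8 of 15, onset Day 14 | 0–11% | 77–99% |

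**Step 4: false pauses.** No true effect, CV 20/10%, at least 5 of all 20 in a group, all draws to Day 336: at most about 0.02% with a 20% cut-off and 0.45% with a 16% cut-off, both under shared errors. A count-only rule at CV 20% would pause about 6% of groups by Day 112, 12% by Day 168 and 50% by Day 336.

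**The case against.** The strongest reply is that this is a design choice, openly stated. Both conditions are in the text, a joint rule is meant to be stricter than either part, and nothing says that it should act at a 30% or 35% selective loss. The 35% benchmark is this review's. That stands, and it is why the point is an improvement.

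Second, the size rests on baseline CD4%, variability and replacement, none of which the protocol gives. Also true. With half the lost cells replaced, the rule detects a 35% loss well. The direction does not depend on these values: any baseline above zero gives a mismatch when replacement is incomplete.

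Third, there are other safeguards. The DSMB sees laboratory results about every 3 months, before each escalation and ad hoc, and may halt the study (Sections 6.4 and 11.6). An unfavourable laboratory change is an adverse event (Section 11.2.1.1). The investigator may stop vaccine (Section 11.5.1), and the trial may be stopped on safety grounds (Section 13.7). A reader might infer that a 35% loss would go unseen; the documents do not support that. These safeguards are discretionary, however, and carry no CD4 number.

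Fourth, a reader might infer that the remedy makes detection near-certain. It does so only when every vaccinee is affected early. With onset at Day 70 the matched cut-off reaches 47–95%.

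**Conclusion.** The point holds as a cheap improvement. With selective depletion, no replacement and baseline CD4% of 35–55%, the two >30% conditions together need a count loss of about 40–49% before noise. A uniform 35% loss from Day 14 is then detected before the dose-4 day with a probability between almost none and about two in three when both conditions must hold at both draws. It is higher if one low CD4% suffices, and lower with later onset or partial uptake. With half replacement the noise-free threshold is 34–37%; with full replacement there is no mismatch. For antibodies that coat cells without depleting them, no CD4% cut-off helps.

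Two stronger readings should be resisted. The rule is not wrong against its own terms, because the protocol sets no detection target. Nor should the CD4% condition be removed: it is what keeps count noise from pausing groups falsely.

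**What to change.** In both Section 6.4.1 item 1 and Section 7.3.3:

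- Keep the CD4% condition, and say that it is a relative decline from baseline required at both confirming draws.
- Set its cut-off to match a 30% count loss: 1 − 0.7/(1 − 0.3p), with p the laboratory's usual CD4%. This gives about 22% at p = 35%, 19% at 45% and 16% at 55%.
- A flat 20% is adequate only up to about p = 50%, where a 35% loss lowers CD4% by 21.2%. At 55% the fall is 19.5%, just short.
- If the sponsor and DSMB prefer to keep 30%, add a sentence saying that the rule then needs about a 40–49% selective loss without replacement.

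The clinical threshold stays with the sponsor and DSMB. The cost is wording in two places and no new blood draws. The downside is slightly more pauses for DSMB review, within the false-pause rates shown in the working.
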